4.5.2. Adverse Events

Adverse events (AEs) will be collected from the start of study intervention until the last follow-up. (Serious) Adverse event ((S)AEs) which are related to protocol required study procedures (e.g. (S)AE related to invasive study procedures) will be recorded as (S)AEs from the signing of the Informed consent form (ICF) (pre-treatment (S)AEs). Any medical occurrences/conditions that begin in the period between signing ICF and the start of study intervention, and which are not related to a protocol-required study procedure, will be recorded on the Medical History/Current Medical Conditions, not as AEs.

All AEs will be summarized using the Medical Dictionary for Regulatory Activities (MedDRA) preferred terms (PT) grouped by system organ class (SOC) (the current version at the time of analysis) and classified into pre-treatment AEs, treatment-emergent (TEAE) and post-treatment AEs. Pre-treatment and post-treatment AEs will be shown by treatment group. Descriptive analysis for TEAEs will be performed for Week 1-12, 13-26, 27-52 and overall week 1-26, 27-52 and 1-52 by study drug.

Incidences of TEAEs and TESAEs per 100 person-years will be summarized by study drug and by study period (weeks 1-12, 13-26, 27-52 and overall elinzanetant for weeks 1-26 and 1-52).

The rate per 100 person-years is calculated as

Rate per 100 person-years = number of subjects with an event / (total drug exposure in years / 100),

where 365.25 days are taken as one year.

A TEAE is defined as any adverse event occurring or worsening on or after the date of the first dose of study drug up to 14 days after the date of the last dose of study drug. AEs will be flagged as TEAE except for AEs for which there is clear evidence that the AE starts before date of first study drug intake (pre-treatment AEs) or after the date of last study drug intake + 14 days (post-treatment AEs).

If the severity of a previously reported event worsens or if the relationship to study intervention/protocol required procedures changes, two separate events should be reported.

Worsening of an AE is defined as follows:

- AE intensity is worsened (e.g. moderate to severe)
- AE changed to a serious event
- AE ends with death

In case an AE starts before the date of last study drug intake + 14 days and worsens after last study drug intake +14 days, it will be considered as two AEs, a TEAE and a post-treatment AE.

Partially missing onset AE date will be imputed following a worst-case approach as described in Section 4.1.1.

version 3.0 Page: 51 of 87

In case of events with different intensity within a subject, the maximum reported intensity will be used. If the same event is considered as both unrelated and related to the study drug within a subject, the event will be reported as related to study drug. If the drug relationship is missing, the event will be considered as being related to the study drug.

The tabulation will follow in principle the Bayer Global Standard Tables catalogue (v4.0 or later). SAEs and Adverse events of special interest (AESI) will be summarized in the same way as described for TEAEs. A separate table summarizing TEAEs that occurred in more than 5% of the subjects will be provided.

In addition, subjects with a COVID-19 as an adverse event will be listed.

Adverse events of special interest (AESI)

AESI will only be identified by Standardized MedDRA Query (SMQ) searches and PTs and AESI 'any condition triggering close liver observation' also via eCRF as further detailed in Section 6.6. The following AEs are included:

- 1. Any condition triggering close liver observation (as listed in Protocol section 10.5)
- 2. Somnolence or fatigue
- 3. Phototoxicity
- 4. Post-menopausal uterine bleeding (women without hysterectomy are considered)

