4.1.1. Handling of Missing Data

This section describes the general handling of missing data. This includes data that would be meaningful for the analysis in terms of the study objectives but were not collected. The rules for handling the data that do not exist or are not considered meaningful for the analysis, because of an intercurrent event, are described in Section 4.2.1 and 4.2.3. No imputation of missing assessments will be performed for the secondary and exploratory endpoints unless it is specified otherwise.

All missing or partial data will be presented in the subject data listing as they are recorded on the eCRF or electronic diary (eDiary).

version 3.0 Page: 21 of 87

For the computation of durations, i.e., time between start and end date of certain events, and concomitant medication intake, a complete date is necessary.

The following rule will be applied to impute the missing start or end date of adverse events (AE)/ concomitant medications (CM)/procedures:

An imputation range will be defined as the earliest possible date (lower range) and the latest possible date (upper range) of the occurrence of AE/CM/procedures. If AE/CM/procedures end date is available, this will be used as the latest possible AE/CM/procedures occurrence date in the imputation range.

If the active treatment start date falls within imputation range, incomplete AE/CM/procedures start date will be imputed as the active treatment start date. If the active treatment start date does not fall within the imputation range, and the placebo treatment start date falls within the imputation range, an incomplete AE/CM/procedures start date is imputed as the placebo treatment start date. Otherwise, the partially missing AE/CM/procedures start date will be imputed to the earliest date of the imputation range. Completely missing start date will not be imputed. According to worst case criteria if there are completely missing AE/CM start dates, those AEs are considered treatment emergent and CMs as concomitant.

Partially missing AE/CM/procedures end date will be imputed as the latest possible date of AE/CM/procedures imputation range. Completely missing end date will not be imputed and presumed to be ongoing.

Missing start dates in certain events (for example date of initial diagnosis) will be imputed by replacing the missing information on the day and month of the event with the first day of the month and the first month of the year.

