4.5. Safety Analyses

4.5.1. Extent of Exposure

The analyses described in this section will be presented for the SAF and the FAS.

Treatment duration will be defined as the number of days from the day of first study drug intake up to and including the day of last study drug intake and will be summarized using descriptive statistics by treatment group and by study drug. For the display by Week 1-12, the treatment duration ends on the end of treatment phase 1 or on the day of last study drug intake, whatever is earlier. For the display by Week 13-26, the treatment duration starts on the first day of treatment phase 2. For the display by Week 27-52, the treatment duration starts on the Visit T9 + 1. The duration of extension period (Part C) starts on the Visit T13 + 1. (As defined in Section 4.1.2.)

The extent of exposure to elinzanetant will be summarized as the total amount of study drug intake in grams and the average daily dose in mg using descriptive statistics per treatment group.

The compliance (as percentage) will be calculated as:

100 * Number of capsules taken / Number of planned capsules

The number of planned capsules is calculated as:

treatment duration * 2

All capsules, including the placebo capsules, will be counted. For participants who withdraw prematurely from the study drug, compliance will be calculated up to the time of last dose. The compliance will be summarized descriptively by treatment group. In addition, percent of compliance will be categorized into 3 groups, less than 80%, 80 to 120% and greater than 120%, and the categories will be summarized by treatment group and by study drug.

Treatment duration will be presented based on the data collected via the eCRF. If the date for end of exposure is not available in eCRF, the last day of drug intake from eDiary will be used to determine the end of exposure. Extent of exposure and compliance will be calculated and presented based on the ePRO daily instrument 'Study drug intake documentation' and on the eCRF 'Drug Accountability' and 'Drug Exposure' pages. The summaries for treatment duration, exposure and compliance will be presented for weeks 1-12, 13-26, 27-52 and overall, (i.e., for the entire 26 (Part A)/52 (Part B) weeks). Treatment duration, exposure and compliance summaries will be shown separately for Part C.

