4.8. Changes to Protocol-planned Analyses

Not applicable.

version 3.0 Page: 59 of 87

5. Sample Size Determination

Approximately 405 participants will be randomly assigned to study intervention in a 2:1 ratio. Of these, 270 participants will be randomly assigned to elinzanetant and the other 135 participants will be randomly assigned to the placebo arm. The randomization will be stratified by women with a personal history of hormone-receptor positive breast cancer or women at high-risk for developing breast cancer (maximum of 10% of participants for high-risk developing breast cancer) and by type of treatment of pre-existing condition at baseline (at least 40% of participants on tamoxifen and at least 40% of participants on aromatase inhibitors in both population groups, i.e. breast cancer and high-risk for developing breast cancer). Assuming a drop-out rate of 10 % in the first 3 months, this will result in approximately 243 evaluable participants in the elinzanetant arm and approximately 122 participants in the placebo arm who completed 12 weeks of treatment. Assuming a yearly drop-out rate of 30% in the elinzanetant arm, approximately 189 participants will be available that were treated for 1 year.

The number of participants needed for this study is based on the total number of participants needed for the safety evaluation. Following the ICH E1 guideline (EMA 1995), a total of 1,500 participants are required that were exposed to at least one dose of elinzanetant 120 mg. Of these 1,500 participants 300-600 should have been treated for at least 6 months and approximately 100 for 1 year. Based on the number of participants that are available from previous phase 1 and phase 2 studies, together with the number of participants that are planned to be enrolled in ongoing and upcoming phase 3 studies, the number of participants needed for the elinzanetant arm in this study is 270, also taking into account that participants in the placebo arm receive elinzanetant after 3 months and the drop-out rates described above.

Assuming a screen failure rate of 50% approximately 810 participants need to be enrolled to achieve the required number of 405 randomized participants. More participants might be enrolled in case the screen failure rate is higher than anticipated. Additionally, further patients may be enrolled in case of an exceptionally high drop-out rate due to a trial-continuity issue.

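### The adverse-event rate per 100 person-years in SAP 4.5.2 is not a first-event rate, and at a 12-week risk of about 5-10% it falls as the window lengthens (minor, cheap to improve)

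*SAP*

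**What the plan says.** SAP 4.5.2 gives the rate as "Rate per 100 person-years = number of subjects with an event / (total drug exposure in years / 100", with a year of 365.25 days. Rates are shown by study drug for "weeks 1-12, 13-26, 27-52 and overall elinzanetant for weeks 1-26 and 1-52". The numerator takes treatment-emergent events "up to 14 days after the date of the last dose of study drug".

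SAP 4.5.1 defines treatment duration as the "number of days from the day of first study drug intake up to and including the day of last study drug intake". Nothing in 4.5.1 or 4.5.2 ends exposure at a first event.

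SAP 4.5.2 adds that "SAEs and Adverse events of special interest (AESI) will be summarized in the same way as described for TEAEs". The special-interest events include somnolence or fatigue, which Protocol Table 2-1 puts at 1-10% of participants in previous studies.

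SAP supplements 1.0 and 2.0 add liver rates whose denominator is time to first event for participants with an event. For those without one it is treatment duration plus later time to the end of observation. The printed formula multiplies events per exposure day by 100, and the following text gives the unit as 100 person-years of 365.25 days.

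**The concern.** Numerator and denominator in 4.5.2 do not refer to the same time at risk, for two reasons. After her first event a participant can add nothing more to the numerator, yet her later drug exposure stays in the denominator; this lowers the rate, and more so in longer windows. Events in the 14 days after stopping count in the numerator, but those days are not drug exposure; this raises the rate slightly.

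The layout makes this visible. Placebo exists only in weeks 1-12, while elinzanetant also gets overall columns for weeks 1-26 and 1-52. For a fairly common event, a reader who sets the weeks 1-52 elinzanetant rate beside the weeks 1-12 placebo rate would see a lower figure for elinzanetant even if the two hazards were the same. The SAP text does not warn against that comparison.

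**Working it through.** **Inputs from the documents**
- 270 participants on elinzanetant and 135 on placebo (SAP Section 5).
- "Assuming a drop-out rate of 10 % in the first 3 months" and "Assuming a yearly drop-out rate of 30% in the elinzanetant arm" (both SAP Section 5).
- 14-day tail and 365.25-day year (SAP 4.5.2).
- Placebo for 12 weeks, then elinzanetant (Protocol 1.1).

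**Plan's own figures.** The documents state no adverse-event rate that could be reproduced. The design figures do reproduce: 270 x 0.9 = 243, 135 x 0.9 = 121.5 (printed as about 122) and 270 x 0.7 = 189.

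**Assumptions**
- Constant hazard, equal on both drugs.
- A 12-week risk r of 1%, 2%, 5% or 10%. The documented 1-10% is not stated to be a 12-week risk.
- The 10% and 30% dropout applies to drug stopping in both arms, with a constant stopping rate within days 1-84 and within days 85-364.
- Every early stopper gets the 14-day tail, even past a period boundary.
- Completers have no tail at day 84 or day 182. At day 364 the tail is 0 days if all enter Part C and 14 days if none do, which gives the ranges below.
- The 121.5 former-placebo participants join the overall elinzanetant columns from day 85.

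**Formulas**
- Daily hazard h = -ln(1 - r)/84.
- First-event rate = 100 x h x 365.25, the same in every window.
- Probability of an event for a stopper = 1 - exp(-h x (duration + 14)).
- SAP rate = 100 x participants with an event / (drug days / 365.25).

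**Weeks 1-12 at r = 10%.** The first-event rate is 100 x 0.10536/84 x 365.25 = 45.81. Mean drug exposure is 0.1/(0.10536/84) = 79.73 days, and the expected proportion with an event is 0.09665. The SAP rate is 100 x 0.09665/(79.73/365.25) = 44.28, which is 3.3% below the first-event rate.

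**Overall elinzanetant at r = 10%**
- Weeks 1-26: 64.27 participants with an event over 152.6 person-years gives 42.1.
- Weeks 1-52: 116.96 to 120.20 participants over 306.0 person-years gives 38.22 to 39.28.
- Ratio to weeks 1-12: 38.22/44.28 = 0.863 and 39.28/44.28 = 0.887.

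**All risks, per 100 person-years**

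| 12-week risk | First-event rate | SAP, weeks 1-12 | SAP, weeks 1-26 | SAP, weeks 1-52 | Weeks 1-52 / weeks 1-12 |
|---|---|---|---|---|---|
| 1% | 4.37 | 4.42 | 4.39 | 4.34-4.49 | 0.98-1.02 |
| 2% | 8.78 | 8.85 | 8.74 | 8.57-8.85 | 0.97-1.00 |
| 5% | 22.30 | 22.13 | 21.56 | 20.52-21.16 | 0.93-0.96 |
| 10% | 45.81 | 44.28 | 42.13 | 38.22-39.28 | 0.86-0.89 |

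At 1-2% the tail outweighs the first-event effect in weeks 1-12, so the SAP rate sits slightly above the first-event rate.

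**If the hazard is not constant.** Suppose all events fall in weeks 1-12, r = 10% and nobody drops out. A first-event denominator gives 45.8 for weeks 1-12. For weeks 1-52 it gives 100 x 0.1/(0.1/0.4581 + 0.9 x 280/365.25) = 11.0. The SAP formula gives 100 x 0.1/(84/365.25) = 43.5 and 100 x 0.1/(364/365.25) = 10.0. Windows of different length are then not comparable under either denominator.

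**Supplement multiplier.** For an illustrative 6 events in 98,280 days, the printed formula gives 6/98,280 x 100 = 0.0061. The stated unit needs 6/98,280 x 36,525 = 2.23.

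**The case against.** A reader might infer that the formula biases the safety comparison of elinzanetant with placebo. The documents do not support that. Weeks 1-12 by study drug is already planned and is the only window in which placebo exists. With equal exposure there, the ratio of the two SAP rates is simply the risk ratio. No rate ratio or test is planned, and Protocol 9.4.5 makes all safety analyses descriptive. The long columns are labelled as overall elinzanetant.

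A reader might also infer that the long-window rate falls below the placebo rate for every common event. It does not: at a 12-week risk of 1-2%, still within the protocol's range for common, the difference is about zero and can change sign. The 11-14% belongs to the top of that range.

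Other objections have force. Table specifications are held in separate documents (SAP Section 1), so a suitable footnote may exist there. A first-event denominator does not make windows comparable when events come early. It also has to fit the phase dates in SAP 4.1.2, which the model above simplifies. The supplements name their liver rate separately, and the sentence after the formula makes the intended unit clear, so the multiplier is a notation slip.

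What remains is that 4.5.2 mismatches events and time at risk, and that the sponsor already stops time at the first event for the liver rates.

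**Conclusion.** The point holds as a minor one. The 4.5.2 rate is fully specified and reproducible, but it is not a first-event incidence rate. At a 12-week risk of about 5% or more it declines with window length even when the hazard is constant. How far it declines depends on the assumed 12-week risk, constant equal hazard, planned dropout in both arms and the 14-day tail. It also depends on how many completers enter Part C, which is why each weeks 1-52 result is a range. No confirmatory result is affected, and rates of rare events, which will include most individual serious events, hardly change.

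**What to change.** **In SAP 4.5.2**, use 100 x participants with the event / person-years at risk. End each participant's time at her first event of that type in the period or, without an event, at the end of the treatment-emergent window for that period. Three details need a stated rule:
- Period boundaries, reconciled with the phase definitions in SAP 4.1.2.
- Events still ongoing at a boundary, and whether a participant with an earlier event is at risk again in the next period.
- Undated events. SAP 4.1.1 says that "if there are completely missing AE/CM start dates, those AEs are considered treatment emergent", but such an event has no date at which to end her time.

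This would bring 4.5.2 into line with the time-to-first-event approach of the liver rates. Those rates follow event-free participants to the end of observation, so either use one censoring rule for both or label them as different measures.

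**In the text or table footnotes**, state that weeks 1-12 by study drug is the comparison with placebo, and that the overall weeks 1-26 and 1-52 elinzanetant rates are not directly comparable with it. This is needed whichever denominator is used.

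**In the supplements**, write the formula as (participants with event / sum of exposure days) * 36,525.

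**Cost.** Event onset and drug exposure dates are already collected. The full change needs a separate denominator for each event row and period instead of one per column. At 10% risk the stated rates would rise by about 3% in weeks 1-12 (44.3 to 45.8) and 17-20% in weeks 1-52 (38.2-39.3 to 45.8). At 2% risk the weeks 1-12 rate would fall by about 0.8% (8.85 to 8.78). If reprogramming is not feasible, keep the formula, label it as participants with an event per 100 person-years of drug exposure and not a first-event rate, and add the footnotes.

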# 8.1.1.8 Vaginal bleeding diary

The vaginal bleeding diary will be completed only by pre-menopausal women who use tamoxifen monotherapy as adjuvant endocrine therapy and who had in addition a vaginal bleeding in the 3 months prior to the Baseline Visit. The vaginal bleeding diary will be completed only during the placebo-controlled period of 12 weeks. It will be filled in daily using the electronic hand-held device.

The vaginal bleeding diary is a frequently used PRO instrument designed to assess the participant's experience of vaginal bleeding symptoms. The vaginal bleeding diary will be completed daily by the participant each evening in the electronic hand-held device, when the participant is to reflect on her experiences in the past 24 hours. Participants will be asked to rate their vaginal bleeding as follows:

- None (no vaginal bleeding)
- Spotting (less than associated with normal menstruation relative to the participant's experience, with no need for sanitary protection (except for panty liners))
- Light (less than associated with normal menstruation relative to the participant's experience, with need for sanitary protection)
- Normal (like normal menstruation relative to the participant's experience)
- Heavy (more than normal menstruation relative to the participant's experience)

Findings from the vaginal bleeding diary data only need to be documented as an AE, if they lead to a special diagnosis, treatment or to a drop-out.

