# 8.3.6 Adverse Events of Special Interest

The following are defined as AESI in this study, if the event takes place after the first intake of study intervention:

- Any condition triggering close liver observation according to Section 10.5.
  - Any increase in liver enzymes meeting the following criteria needs to be reported as an adverse event to the sponsor within 24 hours of the investigator's awareness for expedited reporting to the health authorities:
    - o ALT and/or AST >8x ULN OR
    - o ALT and/or AST >3x ULN with total bilirubin >2x ULN

The investigator may consider whether the observed increase in liver values would qualify as SAE.

- Somnolence or fatigue: Mild somnolence has been identified as a possible adverse reaction to elinzanetant. Participants will be instructed neither to drive nor operate machinery if they experience somnolence or fatigue. As a precautionary measure, participants are dosed before going to bed.
- Phototoxicity: A signal with respect to potential phototoxicity warrants monitoring of participants for skin reactions to sunlight. In case such a reaction occurs, exposure to strong sunlight should be avoided.
- Post-menopausal uterine bleeding: Any participants experiencing post-menopausal bleeding after randomization should undergo a transvaginal ultrasound with subsequent investigation and management (including endometrial biopsy, if indicated) according to the investigator's clinical judgement and usual practice (unexplained post-menopausal bleeding prior to randomization will exclude the participant from the study).

10 MAY 2023 Page: 57 of 97

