6.6. Appendix 6: Coding conditions applicable for AESI

	ing conditions applicable for AESI
AESI	Search
Potential AESI – Liver event	SMQ Cholestasis and jaundice of hepatic organ
	SMQ Drug related hepatic disorders – severe events only
"Any condition triggering close	SMQ Liver related investigations, signs and symptoms
liver observation" according to	SMQ Liver-related coagulation and bleeding disturbances
protocol Section 10.5 results in	
true AESIs of liver events. The	In addition, include AESIs ticked at AE-CRF.
search specified here is beyond	
the protocol definition of the AESI	
and will be considered together	
with the assessment by the Liver	
Safety Monitoring Board to	
determine a true AESI.	
Somnolence or fatigue	a) Somnolence MLG:
	PT Somnolence
	PT Hypersomnia
	b) Fatigue (MGL Decreased general strength and energy)
	PT Asthenia
	PT Decreased activity
	PT Fatigue
	PT Fatigue management
	PT Mental fatigue
	PT Physical deconditioning
	PT Sluggisheness
	In addition to MLGs above, include PT Sleep disorder due to general
	medical condition, hypersomnia type
Phototoxicity	BMQ Photosensitivity reactions
-	•
Post-menopausal uterine bleeding	
	MLG Female genital tract bleeding
	PT Abnormal uterine bleeding
	PT Abnormal withdrawal bleeding
	PT Cervix haematoma uterine
	PT Cervix haemorrhage uterine
	PT Coital bleeding
	PT Haematocoele female
	PT Haematosalpinx
	PT Haemorrhagic ovarian cyst
	PT Ovarian haematoma
	PT Ovarian haemorrhage
	PT postmenopausal haemorrhage
	PT Unexpected vaginal bleeding on hormonal IUD
	PT Uterine haematoma
	PT Uterine haemorrhage
	PT Vaginal haematoma
	PT Vaginal haemorrhage
	PT Vulval haematoma
	PT Vulval haematoma evacuation
	PT Vaginal haemorrhage
	PT Withdrawal bleed
İ	

version 3.0 Page: 86 of 87

7. References

- Arimidex SmPC. UK Summary of Product Characteristics for Arimidex(Anastrozole), dated 22 Jun 2021. 2021.

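### The AESI of post-menopausal uterine bleeding is restricted by hysterectomy but not by menopausal status, so its count and denominator do not match its label

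*SAP*

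**What the plan says.** Protocol 8.3.6 defines the event by menopausal status: "Post-menopausal uterine bleeding: Any participants experiencing post-menopausal bleeding after randomization should undergo a transvaginal ultrasound".

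SAP 4.5.2 carries it over as "Post-menopausal uterine bleeding (women without hysterectomy are considered". The hysterectomy condition is the only population rule given. On identification, the same section says "AESI will only be identified by Standardized MedDRA Query (SMQ) searches and PTs"; the eCRF is an extra route for the liver event only. AESIs are to be summarized like other treatment-emergent events, for which SAP 4.5.2 also plans rates per 100 person-years of drug exposure.

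The search in SAP 6.6 is headed "MLG Female genital tract bleeding". It includes "PT postmenopausal haemorrhage", but also terms such as "PT Abnormal uterine bleeding", vaginal haemorrhage and withdrawal bleed.

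The population is mixed by design. Protocol 5.1 admits women aged 18 to 70, and Protocol 10.4.2 confirms that women of childbearing potential take part. Protocol 8.1.1.8 sets up a bleeding diary to be "completed only by pre-menopausal women who use tamoxifen monotherapy" and who bled in the 3 months before baseline.

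**The concern.** An AESI rate is read as the risk of the named event in women who can have it. Here the name carries a menopausal condition and the counting rule does not. A programmer who follows SAP 4.5.2 and 6.6 literally would count any listed bleeding term in any woman with a uterus and divide by all such women, or by their exposure.

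Two safety questions are then mixed. Bleeding after menopause is an endometrial question, which is why Protocol 8.3.6 attaches an ultrasound work-up to it. Bleeding changes in menstruating women are a different matter: Protocol 2.3.1 reports that elinzanetant lowered estradiol, progesterone and luteinizing hormone in pre-menopausal females, linked in one study to delayed or irregular menses. No other planned table separates the two groups. Diary data are only listed (SAP 4.4.8), and menopausal status is not among the subgroups in SAP 4.6.2.

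SAP 1.2 describes the study population as post-menopausal, which conflicts with the protocol. On that description no menopausal restriction would be needed, so the omission may be an oversight.

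**Working it through.** **The passages side by side**

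1. *Event.* Protocol 8.3.6: uterine bleeding after menopause.
2. *Who is counted.* SAP 4.5.2: women without hysterectomy. Menopausal status is not mentioned.
3. *What is counted.* SAP 6.6 lists 20 term lines (19 distinct, since vaginal haemorrhage appears twice). One names the post-menopausal event. Most can be coded whatever the menopausal status, and some are not uterine (ovarian haemorrhage, vulval haematoma).
4. *Who is in the trial.* Protocol 5.1, 8.1.1.8 and 10.4.2: pre-menopausal women, some menstruating.

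Items 1 and 2 agree only if every woman with a uterus is post-menopausal, and item 4 rules that out.

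**How much pre-menopausal bleeding can enter the numerator**

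Protocol 8.1.1.8 makes a diary finding an adverse event only when it leads to a specific diagnosis, to treatment or to drop-out. Protocol 10.3.1 also excludes expected fluctuation of a pre-existing condition that does not worsen. Ordinary menstruation should therefore seldom be counted. The diary rule covers only diary keepers in the 12 placebo-controlled weeks, so it reduces the numerator problem without removing it, and it leaves the denominator untouched.

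**Illustration of size**

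The plan states no figure for this event, so there is nothing to reproduce. Let *p* be the pre-menopausal share of women without hysterectomy, and let *r_post* and *r_pre* be the proportions with a captured term in each group. The table then shows

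reported = (1 − p) × r_post + p × r_pre,

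while the label promises r_post. All inputs are assumptions: r_post = 3%, r_pre = 0%, 3% or 10%, and p = 10%, 30% or 50%. The planned 270 women on elinzanetant (Protocol 9.2) are all taken to have a uterus.

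| p | Reported, r_pre = 0% | Reported, r_pre = 3% | Reported, r_pre = 10% | Counted women not post-menopausal, r_pre = 10% | Denominator if restricted |
|---|---|---|---|---|---|
| 10% | 2.7% | 3.0% | 3.7% | 27% | 243 |
| 30% | 2.1% | 3.0% | 5.1% | 59% | 189 |
| 50% | 1.5% | 3.0% | 6.5% | 77% | 135 |

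Example for p = 30%, r_pre = 10%: 0.7 × 3% + 0.3 × 10% = 2.1% + 3.0% = 5.1%, of which 3.0/5.1 = 59% comes from pre-menopausal women. The ratio of reported to target runs from 1.5/3 = 0.50 to 6.5/3 = 2.17. It equals 1 when the two groups have the same rate.

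**The case against.** The strongest reply is that the event's name already carries the menopausal restriction and the bracket only narrows it further. Table specifications are held in separate documents (SAP 1), and a denominator rule may be there. This cannot be excluded. But the SAP spells out one half of the population rule, leaves out the other, and says identification is by search terms only. A title is not a rule that can be programmed.

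A second reply is that a broad search is a sensible, inclusive choice for a safety screen. That stands, and it argues for keeping every term visible by menopausal status, not for pooling the groups under a post-menopausal label.

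A reader might infer more: that the rate is wrong by a known amount, that a real signal will be hidden or a false one created, or that endometrial safety is left unassessed. The documents do not support this.

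- They give no pre-menopausal share and no bleeding rates.
- Because AESIs are tabulated like other events, by preferred term, postmenopausal haemorrhage should appear on its own line.
- In weeks 1-12 the arms are randomized, so the menopausal mix should be similar in both. If pre-menopausal women contributed no events, both arms would be scaled by the same (1 − p) and their ratio would not change.
- Endometrial thickness and three-reader biopsies are analysed separately (SAP 4.5.3.7 and 4.5.3.9), and the SAP supplements split the end-of-treatment and unscheduled results into weeks 1-12 and 13-52.

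These points limit the consequence. They do not make the pooled rate match its name, and after week 12 all women on treatment receive elinzanetant, so the absolute rate is what will be read.

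**Conclusion.** The point holds as a mismatch between definition and counting rule. Followed as written, SAP 4.5.2 and 6.6 give a rate whose denominator includes women outside the defined event and whose numerator can include their bleeding events, with numerator contamination limited by the protocol's reporting rules.

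Neither size nor direction can be derived from the documents. The range of 1.5% to 6.5% around an assumed 3% shows only that the error can go either way, and its upper end uses a 10% pre-menopausal rate that may be high given those reporting rules.

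The consequence is confined to one descriptive AESI presentation. Efficacy tests, type I error and power are unaffected. It is worth correcting because the repair is specific and cheap, and a reader of the pooled rate could not undo the mixing.

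**What to change.** In SAP 4.5.2, or in a supplement to it:

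- Present this AESI, with numerator, subject denominator and exposure-years alike, for women without hysterectomy who are post-menopausal by the Protocol 10.4.1 definition.
- State how amenorrhea induced by GnRH analogues or chemotherapy is classified. Protocol 10.4.1 requires spontaneous amenorrhea and itself treats fertility after chemotherapy as potentially unclear.
- State how a woman whose status changes during the study is handled, so that bleeding after a change to post-menopausal is not dropped.
- Tabulate the same terms separately for the remaining women without hysterectomy, so that no event is lost.
- Correct the population description in SAP 1.2.

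SAP 6.5.2 already lists years of amenorrhea and prior hysterectomy or oophorectomy, but no menopausal-status variable, so a flag must be derived. Its oophorectomy terms include unilateral procedures, whereas surgical menopause in Protocol 10.4.1 needs bilateral removal. Years of amenorrhea alone may not separate spontaneous from induced cases, so medication and medical history may be needed as well.

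The cost is the derived flag, a few SAP sentences, one extra table and a smaller denominator for this AESI.
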